DESIGN This is a Phase 1/2, randomized, double blind, two-arm, partial cross-over, single-site, pilot study evaluating the effect of oral dipyridamole (DP) on immune activation and inflammation in HIV-1-infected, ART-treated subjects with HIV-1 RNA less than 50 copies/mL. The change from baseline to week 12 in the plasma levels of sCD163 and sCD14, and IL-6 will be assessed within and compared between study arms, as will secondary endpoints related to immune activation, inflammation, gut mucosal changes, pulmonary function and brachial artery flow-mediated dilation (FMD).

Subjects will be randomized 1:1 to DP 100 mg 4 times a day or matching placebo. Following week 12, subjects in the DP arm will continue DP for an additional 12 weeks (for total 24 weeks) and subjects in the placebo arm will cross over to DP 100 mg 4 times a day for 12 weeks.

Evaluations will be scheduled at Entry (week 0) and Weeks 2, 4, 8, 12, 14, 16, 20, 24, and 28.

DURATION Subjects will be in the study for 28 weeks.

[figure not shown]
SAMPLE SIZE 40 subjects, 20 per arm. Rectal Tissue Subset: 20 subjects, 10 per arm.

POPULATION HIV-1-infected male and female subjects, 18 years of age or older, on ART with HIV-1 RNA <50 copies/mL for a minimum of 12 months.

STRATIFICATION Subjects will be stratified by CD4+ T-cell counts (≤ 500 versus > 500 cells/mm³, and by enrollment into the Rectal Tissue Subset)

REGIMEN
Arm A: Dipyridamole 100 mg 4 times daily for 24 weeks
Arm B: Dipyridamole placebo 1 capsule 4 times daily for 12 weeks, then Dipyridamole 100 mg 4 times daily for 12 weeks.

STUDY SCHEMA:

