DP has a vasodilatory effect and should be used with caution in patients with severe coronary artery disease (e.g., unstable angina or recently sustained myocardial infarction). Chest pain may be aggravated in patients with underlying coronary artery disease who are receiving DP. Elevations of hepatic enzymes and hepatic failure have been reported in association with DP administration. DP should be used with caution in patients with hypotension since it can produce peripheral vasodilation.

DP has been reported to increase the plasma levels and cardiovascular effects of adenosine and may counteract the anticholinesterase effect of cholinesterase inhibitors, thereby potentially aggravating myasthenia gravis.

Adverse reactions at therapeutic doses are usually minimal and transient. With long-term use of DP tablets, initial side effects usually disappear. The following reactions in Table 1 were reported in two heart valve replacement trials comparing DP tablets and warfarin therapy to either warfarin alone or warfarin and placebo:

Table 1 Adverse Reactions Reported in 2 Heart Valve Replacement Trials

| Adverse Reaction | Dipyridamole Tablets/Warfarin | Placebo/Warfarin |
|-------------------------|--------------------------------------|-------------------------|
| Number of Patients | 147 | 170 |
| Dizziness | 13.6% | 8.2% |
| Abdominal distress | 6.1% | 3.5% |
| Headache | 2.3% | 0.0% |
| Rash | 2.3% | 1.1% |

Other reactions from uncontrolled studies include diarrhea, vomiting, flushing and pruritus. In addition, angina pectoris has been reported rarely and there have been rare reports of liver dysfunction. On those uncommon occasions when adverse reactions have been persistent or intolerable, they have ceased on withdrawal of the medication.

When DP tablets were administered concomitantly with warfarin, bleeding was no greater in frequency or severity than that observed when warfarin was administered alone. In rare cases, increased bleeding during or after surgery has been observed. The

guidelines from the American Society of Gastrointestinal Endoscopy state that low risk endoscopic procedures, including flexible sigmoidoscopy with biopsies, may be performed on patients using standard-dose DP or ASA-DP combinations.⁴³

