5.1.3 Study Treatment Duration

Subjects will remain on study treatment until Week 24.

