6.2.4 Discontinuation Evaluations

Evaluations for Randomized Subjects Who Do Not Start Study Treatment

Subjects who are randomized but do not start study treatment within 72 hours will be taken off study with no further evaluations required. All case report forms (CRFs) must be completed for the period up to and including week 0.

Premature Treatment Discontinuation Evaluations

Subjects who prematurely discontinue study treatment will have a study discontinuation visit as per Section 6.1 and then be taken off study.

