6.3.5 Clinical Assessments

Complete Physical Examination

A complete physical examination is performed at Screening and is to include at a minimum an examination of the skin, head, mouth, and neck; auscultation of the chest; cardiac exam; abdominal exam; examination of the extremities for edema. The complete physical exam will also include signs and symptoms, diagnoses, height, weight, and vital signs (temperature, pulse, respiration rate, and blood pressure).

Targeted Physical Exam

A targeted physical examination is performed at Entry and all other study visits to include weight and vital signs (temperature, pulse, respiration rate, and blood pressure) and is to be driven by any previously identified or new signs or symptoms, or any diagnoses that the subject has experienced within 30 days prior to entry/since the last visit.

Height

Height will be recorded on the CRF at the screening visit only.

Weight

Weight will be recorded on the CRF at each targeted physical exam.

Signs and Symptoms

At entry, all grades that occurred within 30 days before study entry must be recorded; post-entry, only new signs and symptoms Grade ≥ 2 must be recorded on CRFs. Record on CRFs all signs and symptoms that led to a change in treatment, regardless of grade. The source document must include date of onset and date of resolution.

Diagnoses

After entry, record all HIV-related and AIDS-defining diagnoses (Centers for Disease Control and Prevention [CDC] category B and C), and the following non-HIV diagnoses: diabetes mellitus, dyslipidemia, hypertension, hypotension, MI, coronary artery disease (not MI), congestive heart failure, stroke, malignancy, renal insufficiency, liver disease, pulmonary embolism, deep vein thrombosis, peripheral artery disease (including peripheral artery revascularization), chronic obstructive pulmonary disease (COPD), and asthma.

Each diagnosis must include:

- a) Date of diagnosis, and date of resolution
- b) Method of diagnosis

Concomitant Medications

Record new, or discontinued concomitant medications including immune-based therapy, blinded study treatment, prescription drugs, nonprescription drugs, alternative therapies, and dietary supplements since the last visit.

Study Drug Modifications

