9.6 Secondary Analyses

Changes from baseline to week 12 and week 24 in other secondary and exploratory endpoints including measurements of immune activation, systemic inflammation, and residual virus in blood and rectal tissue, change in pre- and post-bronchodilator FEV₁, and percent FMD (see 9.2.2 and 9.2.3) will be summarized by means, medians, standard deviations, and 95% CIs for each of the treatment arms. As in the primary analysis, between-arm comparisons will be made using either an ANCOVA model or the Wilcoxon rank sum test. For secondary outcomes with more frequent measurements (i.e. baseline, 4, 12 week), longitudinal models such as Generalized Estimating Equations (GEE) will be used to compare the trajectories across time between treatment arms. Included in the model will be predictor variables for week, treatment group, and their interaction.

The study design allows for an additional 12 weeks of follow up in which the placebo arm crosses over to DP 100 mg 4 times daily for 12 weeks. As an exploratory measure, the trajectories of T cell activation and IL-6 expression for these subjects will be analyzed using a generalized linear mixed model with covariates for week (defined as time since initiating placebo/DP), drug (placebo/DP), and their interaction. The effects of long-term and short-term DP on T cell activation will be quantified using an ANCOVA model, similar to the primary analysis.

Safety will be evaluated by summarizing the number and frequency of Grade ≥ 2 adverse events within each study arm. Comparisons between study arms will be done

using Fisher's exact test at each study visit.

Statistical significance for each of the secondary analyses will be tested using the nominal 5% type I error rate.

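### In Section 9.6 the Arm B-only crossover model confounds the DP main effect with study period, and the by-visit AE tests run past Week 12, where they no longer compare DP with placebo

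*Combined protocol and SAP*

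**What the plan says.** **Crossover model.** Section 9.6 describes the placebo arm moving to DP after Week 12 and then states that "the trajectories of T cell activation and IL-6 expression for these subjects will be analyzed using a generalized linear mixed model". The terms of that model, three in number, are listed straight afterwards: it is to be fitted "with covariates for week (defined as time since initiating placebo/DP), drug (placebo/DP), and their interaction". The nearest antecedent of the subjects referred to is Arm B. The model is labelled exploratory. The design summary confirms the sequence: "subjects in the placebo arm will cross over to DP 100 mg 4 times a day for 12 weeks". Arm A takes DP throughout Weeks 0-24.

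**AE comparison.** Section 9.6 compares Grade 2 or higher AEs between arms "using Fisher's exact test at each study visit", at a nominal 5%, with no limit at Week 12. Section 5.1.3 says "Subjects will remain on study treatment until Week 24", so both arms are on DP from Week 12 to Week 24 and both are off it at Week 28. Four other statements bear on how the tests read:
- Section 2.3: "With long-term use of DP tablets, initial side effects usually disappear".
- Section 6.3.5: "post-entry, only new signs and symptoms Grade ≥ 2 must be recorded on CRFs".
- Section 6.2.4: "Subjects who prematurely discontinue study treatment will have a study discontinuation visit as per Section 6.1 and then be taken off study".
- Section 6.1 schedules clinical assessments at Weeks 4, 8, 12, 16, 20, 24 and 28, with telephone contacts at Weeks 2 and 14.

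**The concern.** In Arm B the drug indicator is 0 for every sample in the first period and 1 for every sample in the second. The week clock restarts at the switch, so no term in the model carries study time. Any shift in T cell activation or IL-6 between the two periods, whatever its cause, enters the drug main effect. Section 3.0 expects Arm B's second period to help detect a DP effect, so a reader could easily take that coefficient as one.

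The AE tests raise a related problem. Through Week 12 a between-arm test compares DP with placebo. After Week 12 the same test, under the same description, compares Arm A subjects still on DP with subjects who have recently started it. At Week 28 neither arm is on drug. If DP causes early side effects that fade, a per-visit test after the switch could show an excess in the placebo-first arm.

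**Working it through.** **The plan's own figure.** The only power figure is in Section 9.4: 80% power at a standardised difference of 0.909 with 20 per arm. A two-sample t-test at two-sided 5% gives 79.99%, so it reproduces. It concerns the Week 12 sCD14 comparison and is not touched by this point.

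**1. Crossover model**

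*Inputs.* Stored samples for these markers are scheduled at Weeks 0, 4, 12, 16 and 24 within the treatment period (Section 6.1). Subjects cross over following Week 12, so Arm B's Week 12 sample is taken as placebo week 12. Drift sizes are assumptions, because the documents give none.

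*Rank.* In Arm B alone, intercept, restarted week, drug and interaction have rank 4 of 4. Adding a period term leaves rank 4 of 5. Categorical visit plus drug has rank 5 of 6. Drug therefore cannot be separated from period within Arm B, and this needs no assumed values.

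*Linear drift of 0.3 SD per 12 weeks, no DP effect.* Means are 0, 0.1, 0.3, 0.4, 0.6.
- Placebo line: intercept 0, slope 0.3/12 = 0.025 per week.
- DP line through restarted weeks 4 and 12: slope (0.6 − 0.4)/8 = 0.025, intercept 0.4 − 4 × 0.025 = 0.30.
- Drug coefficient 0.30 SD; interaction 0.025 − 0.025 = 0.

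*Rise of 0.3 SD to Week 12, then flat.* The placebo line is as above. The DP line has intercept 0.30 and slope 0. Drug coefficient 0.30 SD; interaction (0 − 0.025) × 12 = −0.30 SD per 12 weeks.

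So the main effect absorbs the drift in both cases, and the interaction is disturbed only in the second, where the slope changes between periods. All values scale with the assumed drift.

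*Both arms.* Use categorical visit (5 means), a common baseline and separate DP effects at 4, 12, 16 and 24 weeks on drug. That is 5 + 4 = 9 parameters. The 10 arm-by-visit cells share one baseline, leaving 9 distinct means, so all effects are estimable. All three of these drifts bias the effects by 0: the two above, and a rise by Week 4 that then stays flat. The SE of the 12-week effect, with n = 20 per arm and correlation ρ between visits, is √[2(1 − ρ²)/20]. At ρ = 0.5 this is √(1.5/20) = 0.274 SD, the same as from Weeks 0 and 12 alone.

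*Pooling all exposure of 12 weeks or more.* This lowers the SE to 0.245 SD at ρ = 0.5, but it assumes a stable effect from 12 to 24 weeks. The bias at ρ = 0.5 from a +0.3 SD departure is:

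| Departure in Arm A | 12-weeks-or-more term | 4-week term |
|---|---|---|
| Week 24 only | −0.12 SD | −0.06 SD |
| Weeks 16 and 24 | −0.06 SD | −0.18 SD |

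**2. AE tests**

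*Visits.* Clinic visits after Week 12 are Weeks 16, 20, 24 and 28, which is 4 of 7. With the telephone contacts it is 5 of 9.

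*Rejection rates.* These use exact enumeration of Fisher's test with 20 per arm and independent visits. AE rates are assumed: 20% or 25% per visit with DP excess, 5% without.
- New events, excess at the first DP visit only. The Week 16 test compares 20% or 25% (Arm B) with 5% (Arm A) and rejects in 16.8% / 29.9%, nearly always with the placebo-first arm worse.
- Cumulative events, sustained excess. Through Week 12, 1 − 0.80³ = 48.8% against 1 − 0.95³ = 14.3% rejects in 56.8% (77.6% at the 25% rate). Through Week 24, 1 − 0.80⁶ = 73.8% against 1 − 0.95³ × 0.80³ = 56.1% rejects in 14.1% (16.9%).
- One test through Week 12 against any of three visit tests, excess at the first visit only. 1 − 0.80 × 0.95² = 27.8% against 14.3% rejects in 10.7%, compared with 17.1%. At the 25% rate it is 17.6% compared with 30.2%.
- Same comparison, sustained excess: 56.8% / 77.6% for the single test, against 42.3% / 65.6%.

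*Scale from the documents.* The largest contrast in Table 1 of Section 2.3 is dizziness, 13.6% against 8.2%, not limited to Grade 2 or higher. At 20 per arm Fisher's test rejects in 2.8%. An observed 3/20 against 2/20 is +5 points, with an exact 95% CI of about −18 to +29, which says more than the p-value.

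**The case against.** The strongest reply is that the plan claims little here. The crossover model is exploratory, in a 40-subject pilot. Section 9.5 already compares IL-6 between randomised arms at Week 12. Section 9.6 plans between-arm comparisons and GEE models for the secondary markers, and an ANCOVA of long-term against short-term DP. Nothing says the Arm B coefficient will be presented as a controlled effect. All of this stands, and it limits the severity.

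The interaction also deserves credit. In an analysis of trajectories it is a natural DP parameter, and a constant secular slope does not bias it. A reader might infer that the whole Arm B model is uninformative; the covariates in Section 9.6 do not support that. A reader might also see an ambiguity in Arm B's single Week 12 sample. The design summary places the crossover after Week 12, so coding it as DP week 0 is unlikely.

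On AEs, Section 9.6 says the comparison is between study arms, not DP versus placebo. Later contrasts are relevant to objective 1.3.5, which covers up to 24 weeks of DP. It would go too far to call them invalid. They answer a different question, longer against newer exposure, and the plan does not say so. That holds whether each test counts new, cumulative or prevalent events, because it follows from the treatment sequence.

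Finally, pooling Arm A's later visits to gain precision assumes the stability that objective 1.3.6 sets out to assess. That objection is accepted, and the pooled term is kept only as a sensitivity analysis.

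**Conclusion.** The point holds at minor to moderate severity.

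The aliasing of drug with period in Arm B is exact and rests only on the treatment sequence and on reading the model as Arm B alone. If both arms were meant, the restarted clock would still leave study visit unadjusted. The size, 0.30 SD for a 0.3 SD drift per 12 weeks, is conditional on an assumed drift and is confined to the main effect unless the slope changes between periods.

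The AE count, 4 of 7 clinic visits, comes directly from the schedule. The rejection rates rest on assumed AE rates and show direction rather than expected results. No general power gain is claimed for a single Week 12 test: it does better for a sustained excess and worse for one confined to the first visit.

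A reader might infer that the trial's main conclusion is at risk. It is not: the primary ANCOVA and its power use the randomised Week 12 comparison only.

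**What to change.** **Crossover model.**
- Fit both arms over Weeks 0-24 with categorical study visit, a common baseline mean and DP effects at 4, 12, 16 and 24 weeks on drug.
- Code Arm B's pre-switch Week 12 sample as placebo, and leave Week 28 out.
- State the assumption of common time effects in both arms, and report the randomised Week 12 contrast beside the model. The benefit is removal of the period bias; there is no SE gain over that contrast.
- A pooled term for 12 weeks or more may be added as a sensitivity analysis only. State its stability assumption, the biases tabulated above, and that subjects who stop treatment leave the study.
- Label any Arm B-only change as an uncontrolled before-after estimate.

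**AEs.**
- Confine DP-versus-placebo inference to one prespecified Fisher test of subjects with at least one new Grade 2 or higher AE from first dose of study product through Week 12, with an exact CI for the difference.
- Report later AEs by time since first DP dose, labelled as longer against newer exposure, with Week 28 shown as off-treatment.

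**Cost.** Wording in Section 9.6 only; no new visits or data. The Arm B result is stated less favourably, AE differences after Week 12 are no longer tested as such, and some power is lost for very early transient AEs (about 11% / 18% against 17% / 30% under the assumed rates).

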1.3 Secondary Objectives

1.3.1 To compare changes in the level of T cell immune activation as measured by the proportion of CD8+ and CD4+ T cells co-expressing HLA-DR and CD38 and the proportion of CD8+ and CD4+ T cell co-expressing CD69 and CD25, after 12 weeks of DP treatment to placebo.

1.3.2 To compare changes in cellular markers of monocyte and macrophage activation, as measured by tissue factor and CD16 expression in monocytes after 12 weeks of DP treatment to placebo.

1.3.3 To compare changes in the levels of systemic inflammatory biomarkers (sTNF α R, TNF α , hsCRP) and levels of coagulation (D-dimer, tissue factor) after 12 weeks of DP treatment to placebo.

1.3.4 To compare changes in brachial artery flow-mediated dilation (FMD) 12 weeks after treatment with DP to placebo.

1.3.5 To evaluate the safety and tolerability of DP administered for up to 24 weeks in HIV-1-infected adults.

1.3.6 To assess persistence of changes in immune activation and levels of systemic inflammation, including the primary endpoint measures, after 24 weeks of DP treatment and 4 weeks after discontinuation of therapy.

1.3.7 To assess whether DP reduces the proportion of cycling CD4+ and CD8+ T cells as measured by Ki-67 expression at baseline and after treatment with DP.

1.3.8 To correlate plasma DP levels to urine adenosine, plasma IL-6, and cellular and soluble markers of immune activation.

1.3.9 To evaluate changes in residual plasma HIV-1 RNA using single copy assay (SCA) before and after DP treatment.

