In post-marketing reporting experience, there have been rare reports of hypersensitivity reactions (such as rash, urticaria, severe bronchospasm, and angioedema), larynx edema, fatigue, malaise, myalgia, arthritis, nausea, dyspepsia, paresthesia, hepatitis, thrombocytopenia, alopecia, cholelithiasis, hypotension, palpitation, and tachycardia.

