4.1 Inclusion Criteria

Subjects must meet all of the following criteria to be eligible for inclusion in the study.

- 4.1.1 HIV-1 infection, documented by any licensed rapid HIV test or HIV enzyme or chemiluminescence immunoassay (E/CIA) test kit at any time prior to study entry and confirmed by a licensed Western blot or a second antibody test by a method other than the initial rapid HIV and/or E/CIA, or by HIV-1 antigen, plasma HIV-1 RNA viral load.

WHO (World Health Organization) and CDC (Centers for Disease Control and Prevention) guidelines mandate that confirmation of the initial test result must use a test that is different from the one used for the initial assessment. A reactive initial rapid test should be confirmed by either another type of rapid assay or an E/CIA that is based on a different antigen preparation and/or different test principle (e.g., indirect versus competitive), or a Western blot or a plasma HIV-1 RNA viral load.

- 4.1.2 Men and women age 18 years or older.
- 4.1.3 On ART for at least 12 months prior to study entry with a regimen that includes three or more antiretroviral medications. Ritonavir used as a pharmacokinetic enhancer for another protease inhibitor will not be counted as an antiretroviral medication.
- 4.1.4 Plasma HIV-1 RNA <50 copies/mL by any standard clinical assay at screening and for a minimum of 12 months prior to entry, confirmed by by at least two measurements prior to study entry, one of which must be at least 48 weeks prior to study entry and one measurement that was obtained between 61 days and 48 weeks prior to study entry. All plasma HIV-1 RNA measurements in the 12 months prior to study entry must be <50 copies/mL (with the exception that a single detectable measurement of ≤ 200 copies/mL is permitted if the RNA levels immediately before and after are <50 copies/mL).
- 4.1.5 Stable ART regimen for at least 8 weeks prior to study entry and no plans to change ART regimen for at least 6 months following study entry.
- 4.1.6 Ability and willingness of subject to provide informed consent.
- 4.1.7 In the opinion of the investigator, no medical, mental health or other condition that precludes participation.

- 4.1.8 Laboratory values obtained within 60 days prior to entry:
- Hemoglobin ≥ 10.0 g/dL
 - Platelet count $\geq 100,000/\text{mm}^3$
 - INR ≤ 1.5 (for rectal tissue subset only)
 - PTT $< 2 \times$ ULN (for rectal tissue subset only)
 - AST and ALT $\leq 2.5 \times$ upper limit of normal (ULN)

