9.2.2 Secondary Endpoints

- Changes from entry to week 12 and 24 (as applicable) in the following:
 - %HLA-DR+ CD38+ expression in CD8+ and CD4+ T-cells
 - %CD69+CD25+ expression in CD4+ and CD8+ T-cells
 - CD16 and tissue factor expression in monocytes
 - Plasma levels of biomarkers of systemic inflammation (sTNF α R, TNF α , hsCRP) and coagulation (D-dimer, tissue factor)
 - Percent brachial artery FMD
 - Proportion of cycling CD4+ and CD8+ T cells as measured by Ki-67 expression
- Grade 2 or higher AEs, treatment discontinuations
- Correlation of plasma DP level to urine adenosine, plasma IL-6, and soluble and cellular markers of immune activation

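### AST and ALT are recorded at every grade but analysed nowhere, so a transaminase rise below Grade 2 that does not change treatment would be missing from the planned safety results

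*Combined protocol and SAP*

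**What the plan says.** Secondary objective 1.3.5 is "To evaluate the safety and tolerability of DP administered for up to 24 weeks in HIV-1-infected adults". Section 9.2.2 gives it one line of endpoints: "Grade 2 or higher AEs, treatment discontinuations". The analysis in 9.6 reads "Safety will be evaluated by summarizing the number and frequency of Grade ≥ 2 adverse events within each study arm", and the arms are compared by Fisher's "exact test at each study visit".

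Section 2.3 warns that "Elevations of hepatic enzymes and hepatic failure have been reported in association with DP administration", and 7.1.2 gives AST and ALT their own management rules. Under 6.1, liver tests are taken at Screening, Entry, weeks 4, 12, 16 and 24, and at premature discontinuation. Under 6.3.6, most post-entry laboratory results reach the CRF only at Grade 2 or higher, or if they changed treatment. AST and ALT, with creatinine and fasting lipids, are exceptions and are kept at any grade. Neither AST nor ALT appears in 9.2.1, 9.2.2, 9.2.3 or 9.6.

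**The concern.** The protocol identifies a liver risk and takes the trouble to keep every AST and ALT value, then reports safety through a threshold that most of those values will not cross. Followed as written, the final report could show no difference in Grade 2 or higher events or in discontinuations while transaminases rose on DP. For a pilot meant to inform later use of the drug in people on ART, that would be an incomplete answer to objective 1.3.5, with the missing information already in the database.

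**Working it through.** **Tracing the data.** The continuous summaries in 9.5 and 9.6 cover the listed primary, secondary and exploratory outcomes, so they do not bring AST or ALT in. A rise that stops treatment is captured as a discontinuation at any grade. A rise to Grade 2 or higher may be captured as an AE. What remains is a rise below Grade 2 that does not stop treatment; it enters no planned safety result.

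**The plan's own figures.** There is no safety calculation to reproduce. The only power figures, in 9.4, do reproduce: a two-sample t test at two-sided 0.05 with 80% power gives a detectable difference of 0.909 SD with 20 per arm and 0.961 SD with 18 per arm. Those group sizes are used below.

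**Assumptions.** The documents give no ALT median, SD, correlation or grade limits. Base case: Entry median 0.6 × ULN, SD of log ALT 0.4, Entry-to-visit correlation 0.5, Grade 1 from 1.25 × ULN, Grade 2 from 2.5 × ULN. Ranges: median 0.5–0.7, log SD 0.3–0.5, Grade 2 cut 2–3 × ULN, Grade 1 cut 1.0–1.5 × ULN.

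**What Fisher's test needs.** With 20 per arm, 4 v 0 gives p = 0.106 and 5 v 0 gives p = 0.047.

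**Scenario 1: ALT rises 1.5-fold in every DP subject.**
- Chance of Grade 2 at a visit = 1 − Φ(ln[cut/(1.5 × median)]/SD).
- Base: ln(2.5/0.9)/0.4 = 2.55, so p = 0.0053. Expected 20 × 0.0053 = 0.11 subjects, and a 90% chance of none.
- Highest corner (median 0.7, SD 0.5, cut 2): ln(2/1.05)/0.5 = 1.29, so p = 0.099. Expected 1.97 of 20; placebo p = 0.018.
- Exact chance that Fisher's p < 0.05 on ALT at a visit: under 0.1% in the base case, 2.9% at the highest corner. Counting AST or ALT (both up 1.5-fold, correlation 0.5–0.7), it is at most 13%.
- Entry-adjusted log ratio: CI half-width = t(0.975, 2n − 4) × SD × √(1 − ρ²) × √(2/n). Base: 2.028 × 0.4 × √0.75 × √0.1 = 0.222, a factor of 1.249. The CI around 1.5 is about 1.20 to 1.87 and excludes 1 in 95% of trials.
- Least precise case (18 per arm, SD 0.5, ρ 0.5): factor 1.342, CI 1.12 to 2.01, excludes 1 in 78%.

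**Scenario 2: ALT triples in 4 of 20 DP subjects and is unchanged in 16.**
- Grade 2: 4 × [1 − Φ(ln(2.5/1.8)/0.4)] + 16 × 0.0002 = 4 × 0.206 + 0.003 = 0.83 subjects (range 0.0 to 2.4).
- Mean ratio = exp(0.2 × ln 3) = 1.25.
- Simulating the adjusted analysis in the base case, the average CI is about 0.92 to 1.70 and excludes 1 about 22–24% of the time.
- Grade 1 or higher on DP: 4 × 0.819 + 16 × 0.033 = 3.8; on placebo: 20 × 0.033 = 0.7. The range is 2.0 v 0.0 to 7.5 v 4.8. Fisher's test on these counts reaches p < 0.05 about 12% of the time in the base case, and 4 v 1 gives p = 0.34.

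**Chance findings from the fix.** Two enzymes at two visits give four differences. If independent, 1 − 0.95⁴ = 0.185.

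**The case against.** The best reply is that the harm described in 2.3 is rare liver dysfunction, with side effects mostly slight and passing. That points to a few affected subjects, which is scenario 2, and there the adjusted comparison performs poorly. This stands: the 95% figure belongs to a uniform shift that has no source in the documents, and should not be read as the general sensitivity of the method. It is also fair that the shift table would not reach significance by the standard applied to the Grade 2 count. Its value is to display a pattern.

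Monitoring is a second reply. Section 9.7 gives the IDSMB toxicity summaries by arm with no stated grade limit, and reported AEs of any grade are reviewed. Some low-grade rises may be seen there. But the quarterly by-arm report cuts laboratory abnormalities at Grade 2, and monitoring is not the reported safety result.

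Third, the values are on file and 9.6 does not forbid extra tables. True, and it lowers the stakes; naming the tables in advance simply makes sure they are produced.

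A reader might infer three stronger points, none of which the documents support:
- **The AE count ignores subjects' state at Entry.** For signs and symptoms, 6.3.5 records only new ones after entry. Section 4.1.8 admits AST and ALT up to 2.5 × ULN, but whether a small further rise in such a subject counts as an AE depends on a grading table that is cited and not reproduced.
- **Blood pressure and pulse need the same between-arm comparisons.** Section 2.3 does say "DP should be used with caution in patients with hypotension since it can produce peripheral vasodilation", and these values are also unanalysed. But their CRF entry rests only on the general rule in 6.3, readings are not timed to dose, and the CI half-width for systolic pressure would be about 6.7 mmHg (4.6 to 8.8 under assumed SDs of 10–15 mmHg). They would add nine comparisons for little information.
- **Subjects are left unprotected.** The rules in 7.1.2 act on individual results and do not depend on 9.6.

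**Conclusion.** The point holds for AST and ALT: a named risk is measured and kept at every grade, yet a rise below Grade 2 that does not change treatment appears in no planned safety result. How much the fix gains depends on the shape of the effect. For a uniform rise the gain is large; for a large rise in a few subjects it is mainly descriptive. All sizes rest on assumed ALT distributions and grade limits. The primary analysis is untouched, so this is a minor improvement to objective 1.3.5.

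**What to change.** Add to 9.6, for all subjects who took study drug and labelled descriptive:

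1. A by-arm shift table of worst on-treatment AST and ALT grade, including Grade 1, against Entry grade through week 12. Include unscheduled repeats under 7.1.2 and discontinuation-visit values, flagging any taken after a drug hold.
2. By-arm change from Entry in log AST and log ALT at weeks 4 and 12, with Entry-adjusted differences, 95% CIs and the number contributing per arm. Subjects who stop treatment leave the study (6.2.4), so give the reason for each missing value.
3. Weeks 12–24 summarised separately as within-subject change (Arm B from week 12, Arm A from Entry), because both arms are then on DP.

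Leave out blood pressure and pulse comparisons. The cost is a paragraph and a few tables, with no new visit, sample or CRF field. The downside is four unadjusted differences, with about a 19% chance, if independent, that at least one CI excludes no difference by chance; the descriptive label answers that.
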